To evaluate the preliminary safety and tolerability of BMS-986249 in combination with nivolumab (Arm C and Arm F) relative to ipilimumab in combination with nivolumab (Arm D) in participants with previously untreated, unresectable or metastatic melanoma	• Incidence of treatment-related Grade 3-5 AEs within 24 weeks
To evaluate the preliminary efficacy of BMS- 986249 in combination with nivolumab (Arm C and Arm F) relative to historic nivolumab monotherapy data in participants with previously untreated, unresectable or metastatic melanoma	ORR as assessed by investigator using RECIST v1.1
Secondary	
To assess the anti-tumor activity of BMS-986249 in combination with nivolumab (Arm C and Arm F) and ipilimumab in combination with nivolumab (Arm D) in participants with previously untreated, unresectable or metastatic melanoma	ORR, DOR, PFS, and TTR as assessed by investigator using RECIST v1.1
To assess the safety and tolerability of BMS- 986249 in combination with nivolumab (Arm C and Arm F), and ipilimumab in combination with nivolumab (Arm D) in participants with previously untreated, unresectable or metastatic melanoma	Incidence of AEs, SAEs, AEs leading to discontinuation, death, and laboratory abnormalities
To characterize the PK of BMS-986249 when administered in combination with nivolumab	 Summary measures of PK parameters of BMS-986249 in combination with nivolumab
To evaluate time to deterioration (TTD) in Quality of Life (QoL) and physical functioning	• TTD as defined by a minimally important decrease from baseline ≥10 points on the EORTC QLQ-C30 global health status/quality of life subscale (items 29 & 30) and Physical Functioning Scale (items 1 to 5)
Exploratory	
To explore the associations between PK of BMS-986249, ipilimumab and nivolumab, safety, efficacy, and clinical biomarkers such as, but not limited to T cell-specific genes	Association measures between BMS986249, ipilimumab, and nivolumab PK levels, select outcomes, and biomarkers of interest
BMS-986249, ipilimumab and nivolumab, safety, efficacy, and clinical biomarkers such as, but not	ipilimumab, and nivolumab PK levels, select

Protocol Amendment No.: 09

Date: 14-Mar-2023 78

Table 4-2: Objectives and Endpoints: The Dose Expansion Phase in Melanoma (Part 2A)

Objectives	Endpoints	
To characterize the immunogenicity of BMS-986249, ipilimumab and nivolumab	Incidence of ADA to ipilimumab, nivolumab, and BMS-986249	

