5.4 Scientific Rationale for Study Design

BMS-986249 is being investigated in humans with advanced solid tumors either as monotherapy or in combination with nivolumab.

5.4.1 Rationale for the BMS-986249 Monotherapy Dose Escalation (Part 1A) and the Safety Evaluation of Combination Doses of BMS-986249 with Nivolumab (Part 1B) Design

The projected human efficacious dose of BMS-986249 is based on the comparable exposure-efficacy relationship observed for BMS-986249 and ipilimumab in nonclinical models. The human efficacious dose of BMS-986249 is projected to be 3 mg/kg (240 mg flat dose), the same as ipilimumab's approved clinical monotherapy dose. The safety of ipilimumab has been extensively characterized in more than 28,686 participants with different cancer types (refer to the ipilimumab IB for further details¹⁵). In nonclinical experiments, BMS-986249 was well tolerated at doses up to 50 mg/kg, with evidence of pharmacodynamic effects at all doses. Thus, this study will evaluate dose escalation of BMS-986249 at planned flat doses of 800, 1,600, and 2,400 mg. Additional de-escalation doses may be tested.

Furthermore, the study plans to evaluate different dose escalations of BMS-986249 in combination with nivolumab. The combination study design and the doses are based on the results of safety data from clinical trials evaluating nivolumab and ipilimumab combinations (CheckMate 067¹,

012,²⁰ and 016¹⁹). The study will evaluate BMS-986249 in combination with 480 mg nivolumab (flat dose) as outlined in the study design schematic in Figure 5.1-1.

Modifying the ipilimumab structure with a Probody mAb has the potential to offer decreased systemic absorption, which may translate into better tolerability but similar efficacy with ipilimumab. Furthermore, the PK data will be evaluated to ensure that there is evidence of decreased systemic absorption.

Given that BMS-986249 shares the structure and properties of ipilimumab, the population in this study includes participants naive to checkpoint inhibitors in order to minimize bias when evaluating safety and efficacy.

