5.4.7.2 Rationale for Nivolumab Monotherapy as a Reference

In 2 distinct Phase 3 trials, nivolumab monotherapy demonstrated clinical benefit in participants with previously untreated unresectable or metastatic melanoma. ¹² In the Phase 3 trial, CA209066, 3 mg/kg nivolumab monotherapy demonstrated an ORR of 40%, significantly greater than that of dacarbazine alone (14%). ²⁷ In study CA209067, 3 mg/kg nivolumab monotherapy achieved an ORR of 45%, this was numerically lower than ipilimumab in combination with nivolumab, but significantly greater than that of ipilimumab alone. This pattern of response rate was consistent regardless of PD-L1 expression levels (see Table 5.4.7.2-1). ¹²

Table 5.4.7.2-1: CA209067 ORR Result Summary by PD-L1 Expression

	nivolumab (N=316)	nivolumab in combination with ipilimumab regimen (N=314)	ipilimumab (N=315)
Objective Response	141 (45%)	185 (59%)	60 (19%)
ORR by tumour PD-L1 expression < 1%	35%, n=41/117	55%, n=68/123	19%, n=21/113
ORR by tumour PD-L1 expression ≥ 1%	55%, n=94/171	65%, n=101/155	19%, n=31/164

Abbreviations: ORR = objective response rate; PD-L1 = programmed death ligand-1.

In both CA209066 and CA209067, the incidence of AEs was lowest in the nivolumab group, most AEs were low-grade (Grade 1-2) with relatively few drug-related high-grade AEs (Grade 3-4, 15% in CA209066 and 16% in CA209067, see Table 5.4.7.1-1). In addition, the safety profile was consistent with that seen in other tumor types. ^{24,27} These data resulted in nivolumab being approved for use by the U.S. FDA in 2014, Marketing Authorization in Europe in 2015, and additional regions for the treatment of metastatic melanoma. ¹²

Nivolumab monotherapy was initially chosen as a reference arm in Part 2A because it may have allowed for a contemporaneous assessment of the contribution of components and therapeutic index of BMS-986249 in combination with nivolumab.

The dose and schedule of 480 mg nivolumab administered IV Q4W is based on the approved recommended dose in advanced melanoma.²⁶

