- viii) Participants with RCC:
 - 1) Participants must have received at least 1 but not more than 2 prior anti-angiogenic therapy regimens (including but not limited to sunitinib, sorafenib, pazopanib, axitinib, tivozanib, and bevacizumab) in the advanced or metastatic setting. Prior cytokine therapy (eg, IL-2, IFN-α), vaccine therapy, or treatment with cytotoxics is allowed.
 - 2) Participants must have received no more than 3 total prior systemic treatment regimens in the advanced or metastatic setting and must have evidence of progression on or after the last treatment regimen received and within 6 months prior to study enrollment.
- e) The BMS-986249 in combination with Nivolumab Randomized Cohort Expansion in Melanoma (Part 2A):
 - i) Histologically confirmed melanoma (per AJCC staging system) that is unresectable or metastatic (Refer to Appendix 11).
 - 1) Participants with ocular melanoma are excluded.
 - ii) No prior systemic anti-cancer therapy for unresectable or metastatic melanoma.
 - 1) Prior adjuvant or neoadjuvant melanoma therapy is permitted if it was completed at least 6 weeks prior to randomization, and all related AEs have either returned to baseline or stabilized.
 - a) Anti-PD-(L)1 therapy with at least 6 months between the last dose and date of recurrence is allowed.
 - 2) Participants must be naive to treatment with an anti-PD-L2, anti-CD137, or anti-CTLA-4 antibody, or any other antibody or drug targeting T cell co-stimulation or checkpoint pathways.
 - iii) In order to be randomized, a participant must have quantifiable PD-L1 expression (≥ 1% or < 1% tumor cell membrane staining) or be classified as PD-L1 indeterminate. Tumor PD-L1 expression will be centrally assessed prior to patient randomization. (Refer to Table 2-1, Section 9.8.2, and the Laboratory Manual).
 - iv) Known BRAF V600 mutation status as determined by local institutional standard or participant consent to BRAF V600 mutation testing per local institutional standards during the Screening Period, the results of which must be reported within 3 months of randomization. All BRAF statuses (BRAF wild-type or BRAF 600 mutation positive) are eligible.
 - v) Prior radiotherapy must have been completed at least 2 weeks prior to study treatment administration.

- f) The BMS-986249 in combination with Nivolumab Additional Tumor Cohort Expansion (Part 2B):
 - i) Cohort 1:Participants with HCC

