The final analysis will take place when all randomized participants have completed at least 36 weeks follow-up or discontinue earlier. Due to exploratory nature of the proof of concept (PoC) design, no multiplicity adjustment will be made for testing multiple endpoints or multiple treatment arms.

10.1.2.2 Changes to Sample Size Assumptions for Revised Protocol 07

[figure not shown]
The original sample size calculation was based on a 60% two-sided CI of ORR for the difference between treatments and required 54 participants per arm. As participants in Arm E will not be randomized as originally planned, the efficacy evaluation and the statistical comparison will use a reference value of based on nivolumab monotherapy historical data in melanoma (see Section 5.4.7.2).

One of the main objectives of this study is to evaluate the preliminary safety and tolerability of BMS-986249 in combination with nivolumab (Part 2A Arm C and Arm F).

Based on final analysis of CA209511, the ipilimimab 3 mg/kg in combination with nivolumab 1 mg/kg, the incidence rate of drug-related Grade 3-5 AEs within 24 weeks is estimated to be relative improvement in the incidence of Grade 3-5 TRAEs is considered to be clinically relevant.

Using a two group $\chi 2$ test with a 0.10 one-sided significance alpha level, assuming a 1:1 randomization ratio of experimental BMS-986249 in combination with nivolumab containing regimen to control ipilimumab in combination with nivolumab, a sample size of 60 participants per arm will have approximately 70% power to detect a ratio in favor of the alternative hypothesis of compared to the null hypothesis proportion of

The null hypothesis is the ratio of proportions above or equal to 1, the alternative hypothesis is the ratio of proportion is below to 1.

Protocol Amendment No.: 09 Date: 14-Mar-2023

e: 14-Mar-2023

The final analysis will take place when all randomized participants have completed at least 36 weeks follow-up or discontinue earlier. Due to exploratory nature of the PoC design, no multiplicity adjustment will be made for testing multiple endpoints or multiple treatment arms.

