APPENDIX 15 REVISED PROTOCOL SUMMARY OF CHANGE HISTORY

Overall Rationale for Protocol Amendment 08, 22-Feb-2022

The primary reasons for Protocol Amendment 08 are to update and/or clarify the inclusion criteria to align with the current disease state and treatment landscape based on investigator feedback for Part 2.

Additional revisions, including in sections of the Protocol Synopsis, have been made to align the protocol with respect to these changes. This amendment incorporates the changes from approved Administrative Letters 05 and 06, which are indicated in the Document History but not listed in the Summary of Key Changes below.

Summary of key changes for Protocol Amendment 08		
Section Number & Title	Description of Change	Brief Rationale
Figure 5.1-2: Study Design Schematic - Part 2, the BMS- 986249 Cohort Expansion Combination Therapy Phase Section 5.4.9: Rationale for Selecting HCC, CRPC, and TNBC in Part 2B Expansion	Updated the study design figure to include participants with intermediate hepatocellular carcinoma (HCC) in Part 2B Cohort 1 and updated the section on rationale for expanding participant population to intermediate HCC in Part 2B Expansion.	To align with current disease state and treatment landscape.
Section 6.1: Inclusion Criteria	Clarified Inclusion Criterion 2)a).	To clarify measurability for Response Evaluation Criteria in Solid Tumors (RECIST) v1.1 vs Prostate Cancer Working Group 3 (PCWG3) criteria.
	Clarified Inclusion Criterion 2)e)ii)1) and 2).	To support melanoma participants given recent changes in adjuvant standard of care.
	Modified Inclusion Criterion 2)f)i)2) and 3).	To support HCC participants given recent changes in first-line treatment landscape.
	Updated Inclusion Criterion 2)f)i)10).	To create consistency across Bristol Myers Squibb (BMS)-sponsored protocols.
	Modified Inclusion Criterion 2)f)ii)3).	To allow for radiotherapy in alignment with recent treatment landscape.
	Added new Inclusion Criterion 2)f)ii)3)c.	To increase clarity.
	Inclusion Criterion 2)f)ii)6) was marked "Not Applicable per Protocol Amendment 08."	To allow for inclusion of Part 2B castration-resistant prostate cancer (CRPC) participants with liver

Protocol Amendment No.: 09

Summary of key changes for Protocol Amendment 08		
Section Number & Title	Description of Change	Brief Rationale
		metastasis based on investigator feedback.
Section 7.4.1: Dose-limiting Toxicities	Modified text in this section.	For increased clarity.

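### The primary ORR reference for Part 2A comes from nivolumab data that probably contain no relapses after adjuvant anti-PD-(L)1, which Part 2A admits, and Section 10 describes no analysis by that exposure

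*Combined protocol and SAP*

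**What the plan says.** Section 6.1, criterion 2)e)ii), requires for Part 2A "No prior systemic anti-cancer therapy for unresectable or metastatic melanoma". Item 1) permits adjuvant or neoadjuvant therapy finished at least 6 weeks before randomization, and item 1)a) reads "Anti-PD-(L)1 therapy with at least 6 months between the last dose and date of recurrence is allowed". Item 2) requires that participants be naive to several named antibody classes "or any other antibody or drug targeting T cell co-stimulation or checkpoint pathways".

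The second primary objective in Table 4-2 assesses ORR in Arms C and F "relative to historic nivolumab monotherapy data in participants with previously untreated, unresectable or metastatic melanoma". Section 10.1.2.2 explains that, because Arm E will not be randomized as planned, the comparison uses a reference value "based on nivolumab monotherapy historical data in melanoma (see Section 5.4.7.2"). The value itself is blacked out. Section 5.4.7.2 cites an ORR of 40% in CA209066 and 45% in CA209067 and says of these trials: "These data resulted in nivolumab being approved for use by the U.S. FDA in 2014".

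Section 5.4.8 stratifies by PD-L1 status and M-stage only. Section 10.3.1 describes ORR estimates with a two-sided 60% CI, a chi-square test and a Cochran-Mantel-Haenszel (CMH) sensitivity analysis. It describes no analysis by prior anti-PD-(L)1. Appendix 15 gives the reason for clarifying the Part 2A prior-therapy criteria in Amendment 08 (February 2022): "To support melanoma participants given recent changes in adjuvant standard of care". Section 5.4.1 states that "the population in this study includes participants naive to checkpoint inhibitors in order to minimize bias when evaluating safety and efficacy".

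**The concern.** A fixed historical reference is fair only if it estimates what nivolumab alone would achieve in the participants actually enrolled. Part 2A can include people whose melanoma returned after adjuvant PD-1 or PD-L1 blockade. The cited trials probably contain none. If exposed participants respond less often, whatever they are given, an arm's ORR is pulled down while the reference stays where it was. An active regimen could then look no better than nivolumab.

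Arm E would have absorbed such a shift, and it is closed. Section 5.4.7 itself warns that historical controls may not represent current patients. The reading matters because this is a primary objective and Section 5.1.2.4 allows arms to be discontinued on preliminary data.

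**Working it through.** **1. The two populations.** The documents place the reference data early. Section 5.4.7.2 ties them to the 2014 approval and reports CA209067 with at least 60 months of follow-up, which the reference list shows was published in 2019. Enrollment therefore closed by about 2014. That these participants had no prior adjuvant anti-PD-(L)1 is an inference from those dates.

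**2. The plan's own figures.** CA209067 nivolumab: 141/316 = 44.6%, printed as 45%, which is correct. The only stated power, about 70% with 60 per arm at one-sided alpha 0.10, is for Grade 3-5 treatment-related AEs. Its rates are blacked out, so it cannot be reproduced; 55% versus 38.6% is one pair that would give it. No power is stated for ORR against the reference.

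**3. Assumptions.** Reference 45% (40% as an alternative); n = 60 (Section 5.2); true ORR in unexposed participants 58% (the CA209067 combination, Section 5.4.7.1); success if the lower limit of the two-sided 60% CI exceeds the reference. The success rule, the exposed share f and the deficit d are not in the documents.

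**4. Threshold.** The exact lower limit for x responders out of n is the 20th percentile of Beta(x, n − x + 1). For n = 60 it is 43.8% at 30 responders and 45.4% at 31, so a 45% reference needs 31/60. A 40% reference needs 28/60.

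**5. Effect of exposure.** Arm ORR = 58% − f × d. The chance of success is P(X ≥ 31) or P(X ≥ 28), with X binomial(60, arm ORR).

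| Exposed share f | Deficit d (points) | Arm ORR | Success, reference 45% | Success, reference 40% |
|---|---|---|---|---|
| 0, or any | any, or 0 | 58% | 87% | 97% |
| 10% | 10 | 57% | 83% | 96% |
| 30% | 10 | 55% | 74% | 92% |
| 30% | 15 | 53.5% | 66% | 88% |
| 30% | 20 | 52% | 57% | 83% |

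**6. Direction.** Suppose 20% are exposed and respond to nivolumab half as often. The matched reference is then 0.8 × 45% + 0.2 × 22.5% = 40.5%. A regimen no better than nivolumab reaches 31/60 with probability 5%, against 18% when the true ORR equals the 45% reference. The mismatch costs power; it does not create false positives.

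**7. Naive subset.** With 30% exposed, 0.7 × 60 = 42 remain. At a true ORR of 58% and a 45% reference, the chance of success is 72% with the exact CI (23/42 needed) or 82% with the Wald CI (22/42 needed). For all 60 participants at a 10-point deficit it is 74%. The subset does not reliably raise the chance of success. Its value is that it compares like with like.

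**The case against.** The strongest reply is that the size rests entirely on assumptions. No passage gives the exposed share, the deficit, the reference value or a go/no-go rule, and the design is called exploratory proof of concept. The 6-month interval excludes early relapses, presumably the most PD-1-resistant, so the deficit may be small. Arm D is randomized under the same criteria, and Table 4-4 provides CMH odds ratios and differences for ORR, so a population-wide drop should show there too. All of this stands. It limits the size but does not remove the mismatch, because Arm D cannot show whether BMS-986249 adds to nivolumab alone.

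A reader might infer more than the documents support:

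- **That eligibility was widened after the reference was set in Revised Protocol 07 (November 2020).** Appendix 15 describes the Part 2A edit as a clarification, while other criteria are described as modified or new. The prior wording is not available.
- **That the sample size should have been revisited.** It rests on the AE endpoint, not ORR.
- **That the Section 5.4.1 statement was a Part 2A premise that has since failed.** It sits in the Part 1 rationale, and Part 1A itself permits prior anti-PD-1.
- **That no subgroup by prior exposure is planned anywhere.** Section 10 describes none, but it defers further detail to a separate SAP that is not available here.

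**Conclusion.** The mismatch is in the current text, and following Section 10 as written could misread an arm's ORR. The likely error is a false no-go for Arm C or F. On the stated assumptions the chance of success falls by 4 points (87% to 83%) in a mild case and by 30 points (87% to 57%) in a severe one, and not at all if exposed participants respond equally. With a 40% reference the severe case is 97% to 83%. The randomized comparisons with Arm D, including the primary safety comparison, are not affected by the historical mismatch.

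The findings do not justify replacing the primary comparison population. Step 7 shows no dependable gain. Moreover, a late switch in an open-label trial whose sponsor already has access to treatment codes (Section 7.4) would invite a charge of data-driven selection.

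**What to change.** Keep the main ORR analysis in Table 4-4 unchanged. Before database lock, add to Section 10.3.1 and the SAP:

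- (a) a sensitivity comparison of Arms C and F with the historical reference in participants with no prior anti-PD-(L)1, to be read alongside the main result;
- (b) ORR with a 60% CI by prior anti-PD-(L)1 status (yes/no) in Arms C, D and F;
- (c) that status as a subgroup for the C versus D and F versus D ORR comparisons.

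Separately, reconcile item 1)a) of criterion 2)e)ii) with item 2), which read literally conflicts with it, and with the checkpoint-naive statement in Section 5.4.1.

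The cost is a few lines of protocol and SAP text. Prior cancer therapies are already recorded at screening (Table 2-1), so no new data are needed. The downside is a wider CI in the naive subset, for example 42 rather than 60 participants if 30% are exposed.
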